9.2 SAFETY ANALYSIS

The safety data (serious adverse events) – both numbers of subjects and events – will be summarised overall using descriptive statistics.

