1 STUDY FLOW CHART

2 SCHEDULE OF ASSESSMENTS

Study Procedure	Screening Visit 1	Screening visit 2 [†]	Visit 1 (+/- 7 days)	Visit 2 (+/- 7 days)	Visit 3 (+/- 7 days)	Visit 4 (+/- 7 days)
Informed consent	✓					
Inclusion/exclusion criteria	✓					
Neuronavigation Scan		✓				
Motor Threshold Assessment		✓				
7T structural scans	✓					
Randomisation	✓					
Demographics	✓					
BMI	✓					
Family Medical History	✓					
Completion of Symptom Diary ^{††§}		✓	✓	✓	✓	
7T magnetic resonance protocol			✓*		✓*	
Pain, fatigue, and depression severity			✓*	✓	✓*	✓
Measure of disease activity	✓		✓	✓	✓	✓
Sickness Questionnaire			✓*	✓	✓*	✓
Pain confounder questionnaires [§]			✓	✓	✓	✓
Michigan Body Map Regional Pain [§]			✓	✓	✓	✓
Blood sample for immunophenotyping ^{†††}			✓*	✓	✓*	✓
TMS or sham procedure			✓		✓	
Recording of Adverse Events			✓	✓	✓	✓

[†] Screening visit will be conducted at the Centre for Cognitive Neuroimaging, University of Glasgow

^{††} Symptom diary will be completed for the 7 days following each visit

^{†††} Blood sample schedule outlined in 6.4 LABORATORY TESTS

^{*} Procedure will be performed twice; before **and** after TMS/Sham therapy

[§] Option to complete questionnaires remotely to reduce visit length

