As a critical first step, this feasibility study aims to pilot a transcranial magnetic stimulation (TMS) protocol designed to target the L-IPL in RA. We will evaluate its effect employing ultra-high resolution 7T functional and glutamate measures. This novel project will inform a larger study which will aim to provide more robust evidence for the proposed neural pain interface between systemic inflammation and pain. Such knowledge could potentially support the analgesic testing of existing compounds e.g. alternative/augmented immunosuppressants or neural glutamate modulatory agents; and reverse translated in order to more precisely dissect the culprit mechanisms which in turn may inform the development of novel pain therapeutics. Both represent core aims of Versus Arthritis and address critical priorities among the patient populations that we serve.

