8 RISK ASSESSMENT AND ADVERSE EVENTS

8.1 RISK ASSESSMENT

Transcranial magnetic stimulation has been used in a growing number of laboratories worldwide since 1984, however there are some potential adverse effects from TMS. Contraindications will be excluded through careful screening. All precautionary measures will be taken to avoid adverse events and safety guidelines will be rigorously followed. TMS is considered safe for studies in both healthy participants and patients when applied within the safety guidelines and is regarded as having a less than minimal risk to study participants. All contraindications and potential adverse effects will be disclosed to the participants in the Participant Information Sheet.

Common adverse effects:

Headaches and/or Neck Pain: Up to 10% of subjects undergoing TMS experience headaches or neck pain, which are believed to be due to muscle tension. All prior cases of headaches induced by TMS have promptly resolved with a single dose of paracetamol or aspirin. In some cases, TMS may cause facial discomfort on the same side of stimulation.

Hearing Problems: TMS produces a loud clicking sound when the current is passed through the stimulation coil. The peak sound pressure associated with the TMS pulse has been measured in a safety study. At a distance of 10cm and with maximum TMS intensity (100% stimulator output), the TMS pulse creates very brief (< 300 micro-sec) peak sound pressure levels of 110 dB (duration of biphasic TMS pulse: 300 micro-sec). Given that the threshold limits of impact noise would be reached only after 1'000-10'000 pulses per day (based on American Conference of Governmental Industrial Hygienists), the risk of TMS noise is considered small even without hearing protection.

Rare adverse effects:

Syncope: Fainting can occur due to anxiety and psycho-physical discomfort during testing and treatment with TMS. Subjects will be monitored for feeling any signs or symptoms of a pending syncopal event (i.e. feeling "dizzy, lightheaded or going to pass out"). If this is the case, TMS will immediately be stopped and the participant will be assisted.

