Seizures: TMS can cause a seizure; however, this is an extremely rare problem. Fewer than 25 cases have been reported from the thousands of studies conducted internationally and the risk of a seizure from repeated courses of TMS is substantially less than one in a thousand. To make the participants' risk as small as possible, the investigators will follow all precautions that are recommended by the International Society for Transcranial Stimulation and mentioned in the 2008 updated safety guidelines of The Safety of TMS Consensus Group.

Memory: TMS could induce transient and weak changes in memory, attention and other cognitive and mental functions up to maximally an hour after TMS. This is a rare risk.

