8.2 ADVERSE EVENTS (AEs)

An adverse event is any untoward medical occurrence, unintended disease or injury, or untoward clinical signs (including abnormal laboratory findings) in subjects, users or other persons, whether or not related to the investigational medical device.

Note 1 to entry: This definition includes events related to the investigational medical device or the comparator.

Note 2 to entry: This definition includes events related to the procedures involved.

Note 3 to entry: For users or other persons, this definition is restricted to events related to the use of investigational medical devices.

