8.5 RECORDING AND REPORTING OF ADVERSE EVENTS

Reports of non-serious Adverse Events (AE), Serious Adverse Events (SAE), serious adverse device events (SADE) or other errors outside of what is foreseen in the protocol (irrespective if a clinical event has occurred) will be reported to the CI and will be submitted to the Research Ethics Committee (REC) using the Non-CTIMP safety report to REC form.

Only reports of SAEs, non-serious AEs or SADEs that are 1. related to the study (i.e. they resulted from administration of any of the research procedures) and 2. unexpected (USADE) should be submitted.

These should be sent within 15 days of the CI becoming aware of the event. There is no requirement for annual safety reports in addition to the information provided through the annual progress report.

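### Section 9.2 limits the safety summary to serious adverse events shown overall, so the mainly non-serious TMS effects named in 8.1 are not counted and active is not set against sham

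*Protocol*

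**What the plan says.** Section 9.2 is the protocol's whole safety analysis. It gives the scope in a bracket, "The safety data (serious adverse events", and says that numbers of subjects and of events "will be summarised overall using descriptive statistics". No other section plans a safety summary.

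Other sections take a wider view of safety:

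- **Section 2, schedule:** the row "Recording of Adverse Events" is ticked at Visits 1 to 4 and is not confined to serious events.
- **Section 8.1:** under common effects, "Up to 10% of subjects undergoing TMS experience headaches or neck pain". Facial discomfort and hearing problems stand under the same heading, although the noise risk is judged small. Syncope and seizure are listed as rare, and so is a cognitive effect: "TMS could induce transient and weak changes in memory, attention and other cognitive and mental functions".
- **Section 8.2:** of adverse events, "This definition includes events related to the investigational medical device or the comparator". Events after active and after sham stimulation are both in scope.
- **Section 8.5:** non-serious events go to the Chief Investigator, but the filter for the ethics committee is narrow: "Only reports of SAEs, non-serious AEs or SADEs that are 1. related to the study", and also unexpected.

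**The concern.** The trial collects adverse events of every grade under both procedures, and then plans to summarise only the grade least likely to occur. The natural reading of the word overall is that active and sham are pooled, although 9.2 does not say pooled.

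Section 3.2 states that "this feasibility study aims to pilot a transcranial magnetic stimulation (TMS) protocol designed to target the L-IPL in RA", and that the results will inform a larger study. Anyone planning that study will want to know how often the named effects followed active stimulation and how often they followed sham. The sham coil is built to reproduce the clicks and scalp sensations (5.6 and 7.1.5), so some complaints can be expected after either procedure. A pooled count could not separate the effect of stimulation from that of the procedure. Section 9.1 compares the outcomes between active and sham; 9.2 has no such contrast for safety.

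**Working it through.** The protocol gives no safety figure to reproduce. The check compares the sections with one another and then gauges the size of the gap.

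**Step 1: which named effects fall within 9.2?** Section 8.3 defines a serious event by death, life-threatening illness or injury, permanent impairment, in-patient or prolonged hospitalisation, intervention to prevent such harm, or foetal harm.

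| Effect named in 8.1 | Rate given in 8.1 | Ordinarily serious under 8.3? |
|---|---|---|
| Headache or neck pain | up to 10% | No |
| Facial discomfort | none | No |
| Hearing problems | none (risk judged small) | No |
| Syncope | none (rare) | No |
| Transient memory or attention change | none (rare) | No |
| Seizure | substantially below 1 in 1,000 | Possibly |

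Only seizure would plausibly reach the 9.2 summary.

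**Step 2: does another section fill the gap?** Section 8.5 sends the ethics committee only events that are both related and unexpected. The effects listed in 8.1 are expected, so they drop out. Reporting to the Chief Investigator is not a tabulation. The annual progress report (8.5 and section 18) has no stated adverse event table.

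**Step 3: how many events are involved?** Inputs: n = 20 participants (synopsis), each due one active and one sham session (5.6); headache or neck pain p = 0.10, the upper figure in 8.1; p = 0.05 and p = 0.02 as assumed lower values. It is also assumed that the 8.1 rates apply to one active session and that all 20 participants receive it.

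Expected cases = n × p; chance of at least one case = 1 − (1 − p)^n.

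| p | Expected cases | Chance of at least one |
|---|---|---|
| 0.10 (protocol, upper) | 20 × 0.10 = 2 | 1 − 0.90^20 = 87.8% |
| 0.05 (assumed) | 20 × 0.05 = 1 | 1 − 0.95^20 = 64.2% |
| 0.02 (assumed) | 20 × 0.02 = 0.4 | 1 − 0.98^20 = 33.2% |

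If only 16 participants had the active session (assumed), p = 0.10 gives 1.6 expected cases and 1 − 0.90^16 = 81.5%.

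For seizure, with p below 0.001, fewer than 20 × 0.001 = 0.02 events are expected, and the chance of at least one is below 1 − 0.999^20 = 2.0%.

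**Step 4: what could a table support?** If 2 of 20 participants reported headache or neck pain, the exact (Clopper-Pearson) 95% confidence interval would be 1.2% to 31.7%. That is enough for description and not for a formal comparison.

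**The case against.** The strongest reply is that this belongs to the statistical analysis plan. Section 9.1 says that plan governs all statistical aspects. Adverse event tables, and how they are split in a crossover, are often left to it. Section 9.2 does not use the word only, and overall could mean over the whole study. It stands that the plan, which was not available, could add the tables. But 9.2 does not defer to it. It names the events and the level of display, whereas 9.3 expressly leaves the choice of software to the plan. An analysis plan that simply followed 9.2 would tabulate serious events alone. Even on a looser reading of overall, 9.2 states no active and sham split.

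A second reply is that safety is neither an objective nor an endpoint in section 4, that non-serious events still reach the Chief Investigator, and that counts this small decide nothing. All of that is true. It limits the weight of the point, but it does not explain why data that are collected should go unreported.

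A third reply is that the 88% takes the top of a range that 8.1 does not state per session. That is fair, and is why lower rates are shown.

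Finally, every participant also receives single TMS pulses at screening visit 2 for the motor threshold (7.1.2), before either study session. A table by procedure needs a place for events from that exposure. A separate line provides it.

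**Conclusion.** The concern holds. As written, 9.2 covers serious adverse events only, shown overall. The effects that the protocol itself expects most often would go uncounted, and no safety display would separate active from sham. At the protocol's upper rate about 2 headache or neck pain cases are expected after active TMS, with an 88% chance of at least one. At the assumed rates of 5% and 2% the chance is 64% and 33%. These figures assume that the 8.1 rates apply to a single session and that all 20 participants receive active stimulation.

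The gap lies in the analysis and not in the collection of events. No primary or secondary efficacy result is affected. The change should be made because it improves what a pilot can report on tolerability, but the trial does not fail without it.

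**What to change.** Amend 9.2 to summarise all adverse events, serious adverse events and device effects descriptively, as numbers of participants and of events, by the procedure last received (active or sham). The denominator is the participants who received that procedure. Events from the Visit 1 session up to the Visit 3 session go to the first procedure, and later events to the second. Any event after the motor threshold pulses and before the Visit 1 session goes on a separate line. The rule allocates events by time and makes no claim about cause. Tabulate after unblinding, with no formal test. An overall column can stay.

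The cost is about one sentence and one table. Adverse events are already recorded at Visits 1 to 4, but the protocol does not mention onset dates. They must be captured, with the order relative to the session for events on the day of Visit 3, so that each event can be assigned.

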9.3 SOFTWARE FOR STATISTICAL ANALYSIS

The statistical software to be used will be specified in the Statistical Analysis Plan. It is likely to be either SAS 9.4 for Windows, Cary, NC, USA or R version 4.0 (R Core Team (2016). R: A language and environment for statistical computing. R Foundation for Statistical Computing, Vienna, Austria. <https://www.R-project.org/>) or higher versions of those programs.

9.4 SAMPLE SIZE

Although inadequately powered to investigate the specific relationship between pain and the MRI metrics, changes in glutamate concentration and functional connectivity pre- and post-TMS have

previously been measured at 3T in sample sizes of n<20. Likewise, changes in pain experience after rTMS have been reported in studies with sample sizes of n<20.

9.5 MANAGEMENT AND DELIVERY

All files will receive a Digital Object Identifier (DOI), with associated metadata being listed in the University of Glasgow Research Data Registry and the DataCite metadata store. The DOI of each dataset will be included in any publication reporting it, allowing each dataset to be identified and accessed by researchers reading the publication. DOIs will also be linked with appropriate records in the University's publication repository to enhance visibility of datasets

10 TRIAL CLOSURE / DEFINITION OF END OF TRIAL

The trial will end once last participant has completed the last visit.

11 DATA HANDLING

11.1 CASE REPORT FORMS / ELECTRONIC DATA RECORD

An eCRF will be used to collect study data. The eCRF will be developed by the study team using Castor and access to the eCRF will be restricted, with only authorised, site-specific personnel able to make entries or amendments to their participants' data. It is the investigator's responsibility to ensure completion and to review and approve data captured in the eCRF.

Data will be validated at the point of entry into the eCRF and at regular intervals during the study. Data discrepancies will be flagged to relevant members of the research team and any data changes will be recorded in order to maintain a complete audit trail (e.g. reason for change, date change made, who made change).

11.2 RECORD RETENTION

To enable evaluations and/or audit from regulatory authorities, the investigator agrees to keep records, including the identity of all participating subjects (sufficient information to link record), all original signed informed consent forms, serious adverse event forms, source documents, and detailed records of treatment disposition in accordance with ICH GCP, local regulations, whichever is longer. The University of Glasgow as per its Code of Good Research Practice will keep pseudonymised research data for 10 years after the study ends.

12 TRIAL MANAGEMENT

12.1 ROUTINE MANAGEMENT OF TRIAL: TRIAL MANAGEMENT GROUP

The trial will be co-ordinated by the Trial Management Group (TMG). The TMG normally includes those individuals responsible for the day-to-day management of the trial, such as the CI, statistician, project manager, research nurse, and research fellow. The role of the group is to monitor all aspects of the conduct and progress of the trial, ensure that the protocol is adhered to and take appropriate action to safeguard participants and the quality of the trial itself.

13 STUDY AUDIT

This study may be selected randomly for audit by NHS Greater Glasgow and Clyde governance team following the annual audit plan.

14 PROTOCOL AMENDMENTS

Any change in the study protocol will require an amendment. Any proposed protocol amendments will be initiated by the CI following discussion with the TMG and any required amendment forms will be submitted to the REC and sponsor.

The CI will liaise with the study sponsor to determine whether an amendment is non-substantial or substantial. All amended versions of the protocol will be signed by the CI and sponsor representative.

Before the amended protocol can be implemented, favourable opinion/approval must be sought from the original reviewing REC, and Research and Development (R&D) office(s).

15 ETHICAL CONSIDERATIONS

15.1 ETHICAL CONDUCT OF THE STUDY

The study will be carried out in accordance with the World Medical Association Declaration of Helsinki (1964) and its revisions (Tokyo [1975], Venice [1983], Hong Kong [1989], South Africa [1996], Edinburgh [2000], Seoul [2008] and Fortaleza [2013]).

Favourable ethical opinion will be sought from a REC before participants are recruited into this clinical study. Participants will only be allowed to enter the study once they have provided written informed consent or their next of kin have provided written informed assent (if required).

The CI will be responsible for updating the REC of any new information related to the study.

15.2 INFORMED CONSENT

Written informed consent will be obtained from each study participant.

The research nurse or investigator will explain the exact nature of the study in writing, provision of participant information sheet, and verbally. This will include the known side-effects that may be experienced, and the risks of participating in this study. Participants will be informed that they are free to withdraw their consent from the study at any time.

16 INSURANCE AND INDEMNITY

The Pro-BEPP study is sponsored by NHS Greater Glasgow and Clyde. The sponsor will be liable for negligent harm caused by the management of the trial. As employers of the protocol authors, both NHS GG&C and the University of Glasgow will be liable for negligent harm caused by the design of the study. NHS GG&C, as the site of the study, will be responsible for harm caused by the conduct of the study. NHS indemnity is provided under the Clinical Negligence and Other Risks Indemnity Scheme (CNORIS). University of Glasgow clinical trials insurance will apply.

The NHS has a duty of care to patients treated, whether or not the patient is taking part in a clinical trial, and the NHS remains liable for clinical negligence and other negligent harm to patients under its duty of care.

17 FUNDING

The study is supported by Versus Arthritis “Probing the Rheumatoid Arthritis Brain to Elucidate Central Pain Pathways”.

18 ANNUAL REPORTS

Annual progress reports will be submitted to REC on the anniversary of the ethics favourable opinion. A copy of this report will also be sent to the Sponsor.

19 DISSEMINATION OF FINDINGS

In addition to the traditional academic routes of communication and dissemination via peer reviewed publication and national and international conferences, we will also use Research into Inflammatory Arthritis Centre Versus Arthritis (RACE) and Glasgow Arthritis Involvement Network (GAIN) Patient Research Partner (PRP) networks to develop local patient and public involvement (PPI) groups. Supported by Engagement Leads (EL) already in place at each institution, RACE PRPs will form a key part of our communications programme. A PRP member from each institution already attends quarterly centre meetings, accompanied by institutional ELs.

We aim to communicate to the student body in our University via PRP-Student Mentor/Buddy system. Newly appointed PhD students in areas related to this project will be paired with a local PRP volunteer for the duration of their project, ensuring the patient remains at the core of the research and giving the students the opportunity to develop insight and the required skills to communicate their ideas and impact of their work with members of the public.

Local PRP Forum Membership. We will join the local RACE scientific meetings, affording local PRPs the opportunity to interact with the wider RACE community.

Communications support. We will provide lay summaries of the project to the IMID community, as well as contributing to the RACE website. Study Summary results will be available via newsletter. We will ask participants to consent to give their contact details (home /email address) for the purpose of study communication including the dissemination of a newsletter.

